**REVISION HISTORY**

Revision #	Version Date	Summary of Changes	Consent Change?
	8.28.2023	Revision to consent & assent language throughout for consistency	No

PROTOCOL TITLE: Metabolic Response to a High-Fat Challenge in Children and Adolescents.

## 1.0 Study Summary

Study Title	Metabolic Response to a High-Fat Challenge in Children and Adolescents.
Study Design	Clinical trial
Primary Objective	The objective of this study is to classify the metabolome and gene expression response to a high-fat (HF) challenge in children, identifying predictors of the homeostatic response, such as insulin resistance (IR) and cardiorespiratory fitness (CRF).
Secondary Objective(s)	To phenotype body composition, daily physical activity, and habitual dietary intake to quantify modifiable behaviors associated with CRF, with the long-term goal of developing clinical interventions aimed at improving CRF in adolescents to preserve metabolic health.
Research Intervention(s)/ Investigational Agent(s)	High-fat Challenge (Boost Glucose Control with palm oil)
IND/IDE #	N/A
Study Population	DHMC Pediatrics
Sample Size	50
Study Duration for individual participants	Two visits separated by 1-2 weeks
Study Specific Abbreviations/ Definitions	AC – acylcarnitine ADA - American Diabetes Association AED - automated external defibrillator AHA - American Heart Association ASA-24 – Automated Self-Administered 24-h dietary recall BIA - bioelectrical-impedance analyses BMI – body mass index CHaD - Children’s Hospital at Dartmouth-Hitchcock cMetS - continuous metabolic syndrome score CRC – clinical research coordinator CRF – cardiorespiratory fitness CVD – cardiovascular disease DG – diacylglycerols DHMC – Dartmouth-Hitchcock Medical Center FA- fatty acid FA-COOH – dicarboxylic fatty acid GINA - The Genetic Information Non-Discrimination Act HbA1c - hemoglobin A1c HDL – high-density lipoproteins

PROTOCOL TITLE: Metabolic Response to a High-Fat Challenge in Children and Adolescents.

	
HEI - Healthy Eating Index
 
HF – high-fat
 
HOMA-IR - homeostatic model assessment for insulin resistance
 
IGF-1 – insulin growth factor 1
 
IR – insulin resistance
 
LDL- low-density lipoproteins
 
MAP - mean arterial blood pressure
 
OGTT - oral glucose tolerance test
 
OLTT – oral lipid tolerance test
 
PA – physical activity
 
PBMC - peripheral blood mononuclear cells
 
PC – phosphocholine
 
PHI – protected health information
 
SM – sphingomyelin
 
T2D – type 2 diabetes
 
TG – triglycerides
 
VO2max – maximal oxygen consumption
 
WC – waist circumference
 
WWC – Weight & Wellness Center
 
6MWT - 6-minute walk test

--	--

PROTOCOL TITLE: Metabolic Response to a High-Fat Challenge in Children and Adolescents.

## 2.0 Objectives\*

Cardiorespiratory fitness (CRF) in youth is an independent risk factor for type 2 diabetes (T2D) (1) and cardiovascular disease (CVD) (2), and in adulthood, CRF is inversely associated with mortality (3). Only 40% of youth in the United States have a healthy CRF (4), possibly influenced by increased sedentary time (5), decreased moderate-to-vigorous activity (5), increased obesity (6), and lower dietary quality (7). CRF is estimated by measuring maximum oxygen consumption ( $\text{VO}_2\text{max}$ ) during intense exercise, challenging the capacity of the respiratory and circulatory systems to supply oxygen to the skeletal muscles for generation of ATP. CRF is directly related to mitochondrial respiratory capacity and is associated with fatty acid (FA) oxidation (8, 9). Profiling the response of the FA oxidation intermediates, measured by metabolomics, and FA oxidation gene expression, measured within peripheral blood mononuclear cells (PBMC), to a high-fat (HF) challenge may provide a mechanistic link between CRF and risk for T2D and CVD. The primary objective of this study is to challenge mitochondrial FA oxidation via administering a HF meal, assessing the relationship between FA oxidation and CRF in youth (age 8-17 years). *We hypothesize that low CRF will be associated with inefficient mitochondrial beta-oxidation, profiled by medium-chain acylcarnitines (AC), and increased extra-mitochondrial oxidation, profiled by dicarboxylic FA (FA-COOH).* The secondary objective of this study is to assess the relationship between FA oxidation intermediates and measures of insulin resistance (IR), glucose homeostasis, and cardiometabolic risk. *We hypothesize that incomplete mitochondrial beta-oxidation and increased extra-mitochondrial oxidation will mediate the relationship between CRF with metabolic health.* We will test our hypotheses through these aims:

[figure not shown]
**SPECIFIC AIM 1. Determine if CRF is associated with modifiable behaviors including body composition, daily physical activity (PA), and habitual dietary intake.** Children, aged 8-17 years (body mass index (BMI) percentile  $\geq 85\%$  for sex/age, matched with leans [ $5\% \leq \text{BMI percentile} < 85\%$ ],  $n=50$ ), will be recruited. Gold-standard stress testing will use a modified Bruce multistage protocol, increasing both the elevation and speed over time, to measure  $\text{VO}_2\text{max}$ . Body composition will be measured using bioelectrical impedance (Seca, Hamburg, Germany). Over seven days, participants will be asked to wear an ActiGraph accelerometer (ActiGraph, Pensacola, FL) and complete three dietary recalls using Automated Self-Administered 24-h dietary recall (ASA-24). We will assess the interaction between PA and habitual dietary intake, measured by the Healthy Eating Index (HEI) score (10), with  $\text{VO}_2\text{max}$ . We will consider if the interaction between PA and HEI score modifies the linear association between percent fat mass and  $\text{VO}_2\text{max}$ .

**SPECIFIC AIM 2. Following a HF-challenge, assess the relationship between mitochondrial and extra-mitochondrial FA oxidation with CRF.** After an overnight fast, participants will consume the HF-challenge, composed of palm oil supplemented Boost® (15% kcal carbohydrates, 15% kcal protein, 70% kcal lipid). Blood will be sampled via intravenous line at baseline ( $t_0$ ) and after consuming the challenge ( $t_{30}$ ,  $t_{60}$ ,  $t_{120}$ , and  $t_{180}$  minutes) and analyzed for fluctuations in glucose and insulin. Plasma targeted metabolomics will be conducted, profiling AC and FA-COOH metabolites. PBMC will be isolated and mRNA levels of genes related to beta- and omega-oxidation will be determined by qPCR. Fold change calculations and longitudinal trajectories, measured by empirical Bayes time-series analysis (11), will quantify the response of metabolites and expression of genes to the challenge. Mixed

PROTOCOL TITLE: Metabolic Response to a High-Fat Challenge in Children and Adolescents. regression models will determine the association between CRF with FA oxidation metabolite and gene (1) absolute levels, (2) longitudinal trajectories, and (3) ratios (12), considering the influence of age, sex, pubertal status, and BMI percentile.

**SPECIFIC AIM 3. Identify if mitochondrial and extra-mitochondrial oxidation of the HF-challenge mediates the relationship between CRF and metabolic health.** In fasting plasma, we will profile the homeostatic model assessment for IR (HOMA-IR), hemoglobin A1c (HbA1c), and a continuous metabolic syndrome score (cMetS), composed of waist circumference (WC), mean arterial blood pressure (MAP), HOMA-IR, HDL-C, and triglycerides (TG) (13). Linear regression will assess the relationship between VO2 max and the metabolic markers. Mediation analyses will be used to identify if FA oxidation metabolite and gene (1) absolute levels, (2) longitudinal trajectories, and (3) ratios (12) mediates the relationship between VO2 max and the metabolic markers, considering the influence of age, sex, pubertal status, and BMI percentile.

The proposed aims will identify modifiable behaviors associated with CRF in youth and will assess if FA metabolism mediates the relationship between CRF and metabolic health, with the long-term goal of developing clinical interventions aimed at improving CRF in youth to preserve metabolic health (Figure 1).

**Figure 1.** Children (BMI%≥5%) will be recruited (aged 8-17). Assessment of characteristics will include blood sampling (glucose homeostasis), a treadmill maximal aerobic capacity assessment (VO2 max), anthropometrics (height, weight, bioelectrical impedance, waist circumference), 24-hr dietary recall, and habitual physical activity measured by an accelerometer. Individuals will undergo a high-fat meal challenge (15% carbohydrates, 15% protein, 70% lipid) and blood sampling will be collected on an acute time-course.

## 3.0 Background\*

PROTOCOL TITLE: Metabolic Response to a High-Fat Challenge in Children and Adolescents.

Cardiorespiratory fitness is the capacity of respiratory and circulatory systems to supply oxygen to skeletal muscle during exercise for the generation of energy. Beginning in childhood, CRF is predictive of IR and T2D (1), CVD (2), and academic performance (14). There is an intrinsic, nonmodifiable aspect of CRF, influenced by genetics (15, 16), age (17), and sex (18). However, in the past three decades, adolescent CRF has declined (19), with only 40% of youth in the United States (aged 12-15 years) maintaining a healthy CRF (4). Global alterations in behaviors may be influencing the decline in CRF, including increased sedentary time (5), decreased moderate-to-vigorous activity (5), increased obesity (6), and lower dietary quality (7). The American Heart Association (AHA) has recently issued a statement (20) emphasizing the importance of accurately and reliably measuring CRF “to identify youth who would benefit from lifestyle interventions but may have been missed by subjective PA recall, anthropometric measures, or CVD risk factor testing, which are current standards of care.” Profiling maximum oxygen consumption ( $\text{VO}_2\text{max}$ ) during intense exercise is the gold standard measure of CRF. The first objective of this grant proposal is to measure  $\text{VO}_2\text{max}$  using a treadmill protocol and to assess the relationship between CRF and body composition, daily PA, and habitual dietary intake (**Specific Aim 1**), with the long-term goal of developing clinical interventions aimed at improving CRF in youth to preserve metabolic health. There have been no studies to date that considered the cross-sectional interaction between PA, measured by Actigraph accelerometers, and habitual dietary intake, measured by the HEI score (10), on CRF in youth (20). We will consider if the interaction between PA and HEI score modifies the association between percent fat mass and CRF, providing avenues for lifestyle changes in adolescents with overweight and obesity.

To sustain exercise, oxygen is circulated to skeletal muscles to be utilized within the mitochondrial via the electron transport chain, supporting the creation of ATP (reference). Therefore, CRF serves as a measurement of mitochondrial respiratory capacity and has been associated with FA oxidation (8, 9). In rats selectively bred for high running capacity (9), Overmyer et al. demonstrated that CRF is associated with a more rapid mitochondrial protein deacetylation at the initiation of exercise and a more efficient and prolonged oxidation of FA during exercise. The inability to efficiently metabolize FAs is associated with elevated levels of bioactive lipids, such as ceramides and diacylglycerols (DG), which leads to cellular stress, inflammation, and increased risk of T2D and CVD (21). The second objective of this grant proposal is to challenge mitochondrial FA oxidation via administering an acute HF meal, assessing the relationship between FA oxidation and CRF (**Specific Aim 2**). Mitochondria are the central hub of FA oxidation (beta-oxidation); however, the endoplasmic reticulum (omega-oxidation) and peroxisomes (alpha-oxidation) serve as FA oxidation rescue pathways when beta-oxidation is overloaded (22). Using plasma metabolomics during the meal challenge, we hypothesize that low CRF will be associated with inefficient mitochondrial beta-oxidation, profiled by AC, and increased extra-mitochondrial oxidation, profiled by FA-COOH (22, 23). Beta- and omega-oxidation gene expression will be quantified within PBMC; a cell type frequently used in human challenges due to its accessibility and expression being comparable to skeletal muscle tissue (24). There have been no studies to date that have used an acute nutrient challenge to assess the relationship between FA oxidation and CRF. Morris et al. assessed variation in the lipidome in response to an oral lipid tolerance test (OLTT) in healthy adults (n=40) observing differences in production of phosphatidylcholines (PC), sphingomyelins (SM)

PROTOCOL TITLE: Metabolic Response to a High-Fat Challenge in Children and Adolescents. and ceramides related to CRF (25). Profiling FA oxidation intermediates and PBMC gene expression rather than the lipidome will provide a more direct readout of FA efficiency.

In youth, literature widely suggests that insulin regulation and resistance may lead to metabolic alterations inducing the development of CVD (26). IR alters lipid metabolism leading to hyperglycemia and dyslipidemia, evidenced by increased in fasting glucose, TGs, and low-density lipoproteins (LDL) and decreases in high-density lipoproteins (HDL). Currently, the American Diabetes Association (ADA) endorses screening for prediabetes and T2D by profiling the response of glucose to an oral glucose tolerance test (OGTT), in which a 75-gram glucose solution is consumed. However, an OGTT has exhibited notable limitations in the pediatric population, including poor reproducibility (27), potentially advocating for new screening tools to be developed. In our recent review (28), we have assessed how metabolomics can be paired with a nutrient challenge to provide a deeper understanding of the homeostatic ability to adapt to a nutrient load potentially identifying pathways and biomarkers of metabolic health. Previous pediatric metabolomics studies in fasted plasma (23, 29) have suggested that mitochondrial and extra-mitochondrial FA oxidation may be an earlier indicator of IR compared to alterations in glucose metabolism. The third objective of this grant proposal is to determine if FA oxidation metabolites and genes during the HF-challenge are associated with measures of IR (e.g. HOMA-IR), glucose homeostasis (e.g. HbA1c), and a continuous metabolic syndrome score (cMetS), composed of WC, MAP, HOMA-IR, HDL-C, and TG (13) (**Specific Aim 3**). We will determine if the ability to metabolize the HF-challenge mediates the relationship between CRF and the profiled metabolic markers. There have been no studies to date that have considered using a HF-challenge to understand metabolic health in youth. We propose that a HF challenge may complement or enhance the ability of an OGTT to classify adolescents at risk of T2D and CVD.

## 4.0 Study Endpoints\*

PROTOCOL TITLE: Metabolic Response to a High-Fat Challenge in Children and Adolescents.

Variable	Instrument / Measurement	Source	Time Series (minutes)				
			0	30	60	120	180
Aim 1: Cardiorespiratory fitness with modifiable behaviors							
Demographics	Questionnaires	Participant self-report	X				
Anthropometrics	Weight, height, BMI percentile, waist circumference, blood pressure, and BIA results	RA	X				
Dietary recall	ASA-24	Participant self-report	X				
Cardiorespiratory fitness	Maximal oxidative capacity treadmill test	Sports cardiology	X				
Physical activity	Actigraph	actigraph	X				
Aim 2: HF-challenge response with cardiorespiratory fitness							
Metabolic response	Untargeted metabolomics and PBMC gene expression	blood	X	X	X	X	X
Cardiorespiratory fitness	Maximal oxidative capacity treadmill test	Sports cardiology	X				
Aim 3: HF-challenge response with metabolic health							
Metabolic response	Untargeted metabolomics and PBMC gene expression	blood	X	X	X	X	X
Fasting laboratory measures	HbA1C, IGF-1, C-peptide, lipid panel	blood	X				
Response laboratory measures	glucose, insulin	blood	X	X	X	X	X

## 5.0 Study Intervention/Investigational Agent

The shake will be composed of a mixture of BOOST Glucose Control® (Nestlé Products) supplemented with palm oil (**Table 1**). Palm oil contains approximately 50% saturated fatty acids (palmitic acid [FA 16:0] and stearic acid [FA 18:0]) and 40% monounsaturated fatty acids (oleic acid [FA 18:1]). Each participant will consume a volume of liquid equivalent to 25% of their estimated daily caloric needs, calculated by the USDA Dietary Reference Intakes using a moderate activity factor. The investigational agent will only be consumed one time, at the second study visit.

## 6.0 Procedures Involved\*

**Assent and Consent:** A clinical research coordinator (CRC) or study team member will collect consent from at least one parent/legal guardian and verbal assent (ages 8-12 years) or written assent (ages 13-17 years) from the participant via a telehealth appointment prior to their first study visit.

PROTOCOL TITLE: Metabolic Response to a High-Fat Challenge in Children and Adolescents.  
**Protocol – Two Study Visits**

**Study Visit 1:** Participants will arrive at the Clinical Research Unit in Faulkner Building 4M at the Main Campus of Dartmouth Hitchcock Medical Center (DHMC) following a two-hour fast. Consent and assent documents will be available to re-read prior to study visit. A sample of the HF-challenge liquid shake will be available to taste to determine if the adolescents will be willing to participate in Study Visit 2. The CRC or other study team member will collect weight, height, blood pressure, and waist circumference. Each participant will have body composition analyzed using bioelectrical-impedance analyses (BIA).

The CRC or other study team member will transfer the participants and their Parents/Guardians to the Sports Cardiology Unit in Cardiac Services 4A at the Main Campus of DHMC. The CRC or other study team member with CPR and BLS training will acclimate the participant to a treadmill and metabolic cart to undergo a maximal aerobic capacity test, measuring CRF. The maximal aerobic capacity test will use the Bruce Protocol (1), a treadmill multistage incremental protocol. Parents/Guardians will fill out electronic questionnaires about demographics, diabetes family history, and past medical history. Children will fill out electronic questionnaires about puberty status measured by Tanner's Stages.

Participants will be compensated \$25 for the completion of the study visit.

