**Between Study Visit 1 and 2**

Between Study Visit 1 and 2, all participants will receive an Actigraph GT9X triaxial accelerometer to objectively assess habitual physical activity for at least seven days. All participants will complete three dietary recalls detailing foods eaten. The timeframe between Study Visit 1 and 2 will be ~7-14 days.

**Study Visit 2:** Participants will arrive at the Clinical Research Unit in Faulkner Building 4M at the Main Campus of DHMC after an overnight fast ( $\geq 12$  hours). Upon arrival, the CRC or other study team member will collect accelerometers and data will be exported via ActiLife software. A RN will place an intravenous line to collect blood sampling throughout the acute meal challenge. The CRC or other study team member will mix and provide the HF-challenge, containing approximately 15% calories from carbohydrates, 15% calories from protein, and 70% calories from fat. Participants will receive a survey identifying their taste preference for the HF shake. Blood sampling will occur prior to the consumption of the HF challenge and 30, 60, 120, and 180 minutes after the consumption of the HF challenge. The CRC or other study team member will collect a 24-hour dietary recall of the previous day. After drinking the HF challenge, the CRC or other team member will collect a brief survey about the taste preference of the HF challenge. Metabolomics and assays for gene expression will be conducted across the time-course.

Participants will be compensated \$75 for the completion of the study visit.

PROTOCOL TITLE: Metabolic Response to a High-Fat Challenge in Children and Adolescents.  

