**Protocol – One Study Visit**

Participants will receive an Actigraph GT9X triaxial accelerometer to objectively assess habitual physical activity for at least seven days. All participants will complete three dietary recalls detailing foods eaten.

Participants will arrive at the Clinical Research Unit in Faulkner Building 4M at the Main Campus of Dartmouth Hitchcock Medical Center (DHMC) after an overnight fast ( $\geq 12$  hours). Consent and assent documents will be available to re-read prior to study visit. The CRC or other study team member will collect weight, height, blood pressure, waist circumference, and hip circumference. Each participant will have body composition analyzed using bioelectrical-impedance analyses (BIA). Parents/Guardians will fill out electronic questionnaires about demographics, diabetes family history, and past medical history. Children will fill out electronic questionnaires about puberty status measured by Tanner's Stages.

A RN will place an intravenous line to collect blood sampling throughout the acute meal challenge. The CRC or other study team member will mix and provide the HF-challenge, containing approximately 15% calories from carbohydrates, 15% calories from protein, and 70% calories from fat. Participants will receive a survey identifying their taste preference for the HF shake. Blood sampling will occur prior to the consumption of the HF challenge and 30, 60, 120, and 180 minutes after the consumption of the HF challenge. The CRC or other study team member will collect a 24-hour dietary recall of the previous day. After drinking the HF challenge, the CRC or other team member will collect a brief survey about the taste preference of the HF challenge. Metabolomics and assays for gene expression will be conducted across the time-course.

Participants will be compensated \$75 for the completion of the study visit.

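### Waist and blood pressure, two of the five cMetS components, are taken under different conditions in the two visit pathways, and pathway is not a listed covariate

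*Combined protocol and SAP*

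**What the plan says.** **Two-visit pathway (Section 6.0, Protocol – Two Study Visits).** Children come to Visit 1 "following a two-hour fast". There, "The CRC or other study team member will collect weight, height, blood pressure, and waist circumference", and BIA is done. Staff then "acclimate the participant to a treadmill and metabolic cart to undergo a maximal aerobic capacity test, measuring CRF". Visit 2 is about 7–14 days later, "at the Main Campus of DHMC after an overnight fast" of at least 12 hours. It covers the IV line, the shake and the timed blood draws, and lists no repeat of waist, blood pressure, weight or BIA.

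**One-visit pathway (Section 6.0, Protocol – One Study Visit).** The same measures, plus hip circumference, are taken when the child arrives "after an overnight fast" of at least 12 hours, at the visit where the blood is drawn. No treadmill test or 6-minute walk test is listed.

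**Use of the measures (Section 2.0, Specific Aim 3).** The cMetS is "composed of waist circumference (WC), mean arterial blood pressure (MAP), HOMA-IR, HDL-C, and triglycerides (TG". The listed adjustment variables are BMI percentile, pubertal status, sex and age. Visit pathway is not among them.

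**Standardisation.** The Physical Assessment and Bioelectrical Impedance Analysis paragraphs of Section 6.0 set no common fasting state, time of day or order of measurement.

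**The concern.** Waist and blood pressure can vary with recent food and fluid, and blood pressure also with anticipation of a maximal exercise test. If one group of children is measured two hours after eating and shortly before a treadmill test, and another after an overnight fast with no test listed, part of any cMetS difference between the groups may come from the measuring conditions. The score also mixes dates in one pathway: waist and MAP precede the three blood components by one to two weeks, while in the other pathway all five come from one visit.

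At stake is the secondary objective in Section 2.0, relating fatty-acid oxidation intermediates to insulin resistance and cardiometabolic risk, for which Section 3.0 names cMetS. That analysis needs no fitness measurement, so children from both pathways can enter it.

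**Working it through.** The plan gives no figure to reproduce here: no SD, no measurement error, no effect of fasting state, and no power basis for N = 50. The check is a comparison of the text, followed by arithmetic on stated assumptions.

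**Step 1. Conditions side by side (Section 6.0).**

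| | Two-visit | One-visit |
|---|---|---|
| Fast before waist and blood pressure | 2 h | at least 12 h |
| Fast before cMetS blood | at least 12 h | at least 12 h |
| Gap from waist/MAP to blood | about 7–14 days | none (same visit) |
| Time of day of waist/MAP | not stated | tied to a challenge starting 7–10 AM |
| Exercise test listed | yes, after the measures | no |

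HOMA-IR, HDL-C and triglycerides are drawn under the same fasting rule in both pathways. Waist and MAP are not taken under the same rule.

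**Step 2. Which analyses mix pathways.**

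- Percent fat with VO2max (Aim 1), and VO2max with metabolic markers, including mediation (Aim 3): these need a fitness value. The one-visit pathway lists none, so as written they use two-visit children only, all under the two-hour rule.
- Fatty-acid oxidation with cMetS, and descriptive or BMI-group comparisons of cMetS: these can pool both pathways.

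**Step 3. Size in cMetS units.** Assumptions, none from the documents: cMetS is a sum of five z-scores with mean inter-component correlation r = 0.3; between-child SD of MAP is 8 mmHg; the pathway shift in MAP is 2–5 mmHg.

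- MAP shift in SD: 2/8 = 0.25; 5/8 = 0.625.
- SD of the sum: √(5 + 20r) = √(5 + 20 × 0.3) = √11 = 3.32.
- cMetS shift: 0.25/3.32 = 0.08 SD; 0.625/3.32 = 0.19 SD.
- Sensitivity to r: at r = 0 the SD is √5 = 2.24 and the range is 0.11–0.28; at r = 0.5 the SD is √15 = 3.87 and the range is 0.06–0.16.
- If waist and MAP each shift by s SD in the same direction, the score shifts by 2s/3.32. For s = 0.1 to 0.5 this is 0.06–0.30 SD at r = 0.3.

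**Step 4. Noise or bias.** Let a share p of pooled children be in one pathway and let cMetS shift by d SD.

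- If pathway is unrelated to fatty-acid oxidation, the slope is unbiased and the variance of cMetS rises by p(1 − p)d². At p = 0.5 and d = 0.19 this is 0.25 × 0.036 = 0.009, or about 1%. At d = 0.30 it is 0.25 × 0.09 = 0.0225, or about 2%.
- If pathway is related to fatty-acid oxidation, the slope is biased by the pathway shift in cMetS times the regression coefficient of pathway on the oxidation measure. The documents give neither factor.

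**Step 5. Could the data show that no shift exists?** Assume 25 children per pathway and a two-sided 5% test. Power is approximately Φ(d√(n/2) − 1.96), with √(25/2) = 3.54. For d = 0.2 it is Φ(0.71 − 1.96) = 10%; for d = 0.5 it is Φ(1.77 − 1.96) = 42%. A non-significant pathway comparison would not rule out a shift of this size.

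**The case against.** The strongest reply is that the effect is small and its route narrow. Three of five cMetS components are unaffected. The assumed shift is a fraction of an SD. Unless pathway is linked to fatty-acid oxidation, it costs about 1–2% in variance. The share of one-visit children is unknown: the Study Summary describes two visits only, and no text says who follows the one-visit pathway. All of this stands, and it limits the point to a cheap improvement. It does not remove the difference: Section 13.0 sets separate incentives for each pathway, so both are provided for. With no allocation rule, a link between pathway and BMI group or metabolism cannot be excluded.

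A second reply is timing. The latest revision is dated 8.28.2023, and Section 9.0 ends the study in December 2023 with primary analyses during 2023. Changing the visit may reach few children. That stands too, and it is why the model term matters more than the re-measurement.

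A reader might infer four stronger things, none of which the documents support:

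- *That the two groups are not comparable.* An assumed 0.08–0.19 SD does not show that. What differs is the conditions of measurement.
- *That percent fat in Aim 1 is distorted by pathway.* By Step 2 that model uses two-visit children only. It would pool pathways only if the 6-minute walk fallback were given to one-visit children, which the plan does not say. Even then, a percent-fat shift of 0.1–0.5 SD unrelated to outcome, with a 50:50 mix, multiplies the slope by 1/(1 + 0.25d²), that is 0.998 to 0.941.
- *That the endpoint table contradicts Visit 1.* The row "Weight, height, BMI percentile, waist circumference, blood pressure, and BIA results" is marked at time 0, but so are the treadmill test, the accelerometer and the dietary recalls. Seven days of accelerometry cannot occur at challenge minute 0, so for these rows the mark can only mean baseline.
- *That the readings are non-fasting or altered by exercise.* A two-hour fast is required, and the measures are described before the treadmill test. Only anticipation is arguable, and the documents are silent on it.

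**Conclusion.** The point holds in a limited form. Two of five cMetS components are measured under different fasting conditions by pathway, and in two-visit children they are also separated from the blood components by about 7–14 days. The plan neither standardises this nor adjusts for it. The consequence falls on analyses that pool pathways, chiefly fatty-acid oxidation against cMetS. The illustrative 0.08–0.19 SD rests on the assumed MAP shift, MAP SD and inter-component correlation in Step 3. The direction and size of any slope bias cannot be stated, because the documents do not say whether pathway is related to fatty-acid oxidation. This is an avoidable measurement difference that is inexpensive to reduce. It does not invalidate an aim.

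**What to change.** 1. In the two-visit pathway, take waist and blood pressure on arrival at Visit 2, after the overnight fast and before the IV line, and use those values for cMetS. All five components then come from one fasting visit in every child.
2. Leave weight, BIA and whatever the treadmill test needs at Visit 1. Percent fat then stays same-day with VO2max; moving BIA would separate the two Aim 1 variables by 7–14 days.
3. Record pathway and hours since last intake for each child. Put a pathway indicator in every model that pools pathways, including for children already measured.

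Cost: a few extra minutes at Visit 2, no new staff or equipment, and one model degree of freedom. The indicator removes a mean shift between pathways. It does not remove the within-child variation from the 7–14 day gap in children already measured, and it also absorbs any real difference between children in the two pathways, so report pooled results with and without it.
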